3.4 Assessment of Objectives

3.4.1 Immunogenicity

The *primary objective* is to investigate the immunogenicity of Human-cl rhFVIII.

The *primary endpoint* is the incidence of inhibitors within the observation period. For one patient an inhibitor is assessed to be positive if the modified Bethesda assay (Nijmegen modification) results in a titer ≥ 0.6 BU at any time point during the observation period.

Inhibitor activity will be determined centrally at the following time points: At baseline (Screening Visit), every 3-4 EDs until ED 20, every 10-12 EDs or every 3 months \pm 2 weeks after ED 20 (whichever comes first), at study completion; at any time in the case of a suspicion of inhibitor development.

In case of a positive inhibitor result, an inhibitor re-testing using a second separately drawn sample should be performed centrally; the result of the second sample will be taken as the final result for the time point. Low titre inhibitors will be defined as ≥ 0.6 to < 5 BU, high-titre inhibitors will be defined as ≥ 5 BU.

Patients who develop a non-transient inhibitor will have an option to start ITI treatment. Patients developing inhibitors and not starting ITI within one year after inhibitor detection will be

withdrawn from the study. Inhibitors that 'disappear' without any clinical signs or symptoms, where no FVIII dosing increase was required, and that turn back to <0.6 BU within a period of 6 months after first detection are regarded as "transient". Patients who develop such a transient inhibitor will continue regular treatment within the study until they have reached ED 100 or a maximum period of 5 years.

Definition of inhibitor confirmation and time to inhibitor occurrence:

Occurrence of inhibitors:

For these definitions inhibitor titres determined in the central laboratory are considered.

(I1) FVIII:C high titre inhibitor occurrence is confirmed, if

inhibitor level ≥ 5 BU at one time point $t_{1,H}$ and

- inhibitor level confirmed to be ≥ 5 BU at a subsequent* time

point $t_{2,H}$ or

- retest of sample from *any* time point $t_{3,H}$ ($=t_{1,H}, t_{2,H}$ or later) confirmed to be ≥ 5 BU.

* 'Subsequent' in the context of this document always means 'at a later time point' or 'in a later sample', but not necessarily the immediate consecutive visit or sample.

(I2) FVIII:C Inhibitor occurrence in a patient is confirmed, if

- a high titre inhibitor is confirmed according to (I1)

or if

- inhibitor level ≥ 0.6 BU at one time point $t_{1,I}$

and retest of sample from same time point $t_{1,I} \geq 0.6$ BU

and inhibitor level ≥ 0.6 BU at a subsequent time point

or

- inhibitor level ≥ 0.6 BU at one time point $t_{1,I}$

and inhibitor level ≥ 0.6 BU at a subsequent time point

and retest of sample from same time point $t_{2,I} \geq 0.6$ BU

or

- inhibitor level ≥ 0.6 BU at three subsequent time points $t_{1,I}, t_{2,I}$ and $t_{3,I}$
(e.g. if retests are not available).

(I3) An inhibitor is confirmed to be a low titre inhibitor, if

- occurrence of inhibitor of < 5 BU is confirmed (according to I2) but

- occurrence of high titre inhibitor (according to I1) is *never* confirmed during the observation period*

(Note: a low titre inhibitor which turns to a confirmed high titre inhibitor according to definition I1 is solely counted as a high titre inhibitor. Inhibitors initially measured as low titre of < 5 BU and remain low titre (< 5 BU) are defined as low titre inhibitors)

*This condition means that a patient only can be defined as having either a low titre inhibitor or a high titre inhibitor. The patient cannot be counted twice.

These definitions for confirmation of positive inhibitors and for high and low titre inhibitors are considered to be relevant for the overwhelming number of inhibitor occurrences. However, there might be cases where additional information (e.g. when taking the whole sequence of inhibitor testing or additional local lab data into account) may suggest that an inhibitor may be assessed rather high titre than low titre. All inhibitor data will be reviewed during the Data Review Meetings before interim analysis/ final analysis to identify such cases.

Time and number of EDs until inhibitor occurrence:

(I4) The time / number of EDs to inhibitor occurrence is defined

- by the time between ED1 and the date of the first positive inhibitor titre detected in a confirmed

inhibitor patient (I2)

- more exactly : as

minimum {date of $t_{1,H}$, date of $t_{1,I}$ } – date of Day 1 (ED1) (days) ,

or the number of EDs (with injections for any indication) during this time frame (ED1 until day before minimum {date of $t_{1,H}$, date of $t_{1,I}$ })

(Note: If different dates for $t_{1,H}$ and $t_{1,I}$ are available, the earlier date will be taken into account)

Censoring: Time / number of EDs until any inhibitor will be censored for patients without inhibitor at date of last available inhibitor testing

For an analysis “time / number of EDs to inhibitor occurrence” for high titre inhibitors the time defined under (I4) will be applied even if the inhibitor had started as minimum {date of $t_{1,H}$, date of $t_{1,I}$ }. For this analysis patients with confirmed low titre inhibitor will be censored at date $t_{1,I}$, where the low titre inhibitor is first detected.

For an analysis “time / number of EDs to inhibitor occurrence” for low titre inhibitors the time defined under (I4) is $t_{1,I}$. For this analysis patients with confirmed high titre inhibitor will be censored at minimum {date of $t_{1,H}$, date of $t_{1,I}$ } where the high titre inhibitor is first detected.

Peak inhibitor titre:

The peak inhibitor titre for each individual patient is defined as the maximum inhibitor titre measured by central lab at any timepoint during the study. This includes also the results of re-tests.

Inhibitor-free period:

An inhibitor is regarded as confirmed between start date as defined above (Definition “I4”) and the time when the inhibitor titre decreases back to <0.6 BU for the first time, which is to be confirmed by a subsequent measurement of <0.6 BU. If the inhibitor titre does not decrease to <0.6 BU during the study, the period with confirmed inhibitor will be counted until study end. Periods of time without confirmed inhibitor are regarded as “inhibitor-free”.

Prophylactic Treatment

Secondary objective: To assess the efficacy of Human-cl rhFVIII during prophylactic treatment.

Secondary endpoint: Monthly rate of spontaneous break-through bleeds during time of prophylactic treatment assessed as excellent, good, moderate or poor by the following scale:

Excellent: Less than 0.75 spontaneous BE per month.

Good: Between 0.75 and 1 spontaneous BE per month.

Moderate: Between more than 1 and 1.5 spontaneous BEs per month.

Poor: More than 1.5 spontaneous BEs per month.

The time period for prophylactic treatment will comprise the time periods between first prophylactic treatment with *Human-cl rhFVIII* until the administration of the last prophylactic treatment + 14 days or completion visit (whichever comes first) minus time periods from start of a surgery until final assessment of the surgery, and minus time period of on-demand treatment, if any. All spontaneous BEs starting during the time periods for prophylactic treatment defined above will be included. BEs categorized as traumatic or as post-operative will not be included in the primary prophylactic treatment assessment.

Regarding BEs during or after surgery this is a general rule.

However, BEs emerging shortly after surgeries could be independent from the surgery, whereas a surgery-related BE could still emerge after the final assessment of the surgery. Therefore the final assessment of whether or not the BE is related to surgery (i.e. to be categorized as post-operative), and hence will be excluded from the BE incidence calculation for prophylactic treatment, will be made in the data review meeting before final database close.

In addition to the analyses described above, the analyses of bleeding rates will be performed in all patients during inhibitor-free periods.

Study drug consumption data (FVIII IU/kg BW, extrapolated to monthly and yearly usage) per subject will be evaluated.

3.4.2 **Bleeding Episodes (BEs)**

Secondary objective: To assess the efficacy of *Human-cl rhFVIII* during treatment of bleeds

Secondary endpoint: Efficacy assessment of bleeding episodes at end of a BE on a four point scale by the patient's parent(s)/legal guardian(s) (together with the Investigator in case of on-site treatment):

- Excellent:* Abrupt pain relief and/or unequivocal improvement in objective signs of bleeding within approximately 8 hours after a single infusion
- Good:* Definite pain relief and/or improvement in signs of bleeding within approximately 8 – 12 hours after an infusion requiring up to 2 infusions for complete resolution
- Moderate:* Probable or slight beneficial effect within approximately 12 hours after the first infusion requiring more than two infusions for complete resolution
- None:* No improvement within 12 hours, or worsening of symptoms, requiring more than 2 infusions for complete resolution

For all breakthrough BEs occurring during the study period, the following data will be documented or derived:

- Type of BE (spontaneous, traumatic, post-operative, joint, other)
- Site(s) of BE
- Start date and time of occurrence/of noticing the BE
- Severity of the BE (minor, moderate, major, life threatening)
- Date and time of end of BE*
- Treatment details: dates and times, doses, batch numbers
- BE during inhibitor-free time period

- Frequency of BEs per patient
- Number of infusions needed to treat a BE per patient
- Study drug consumption (FVIII IU/kg BW per infusion, per BE, per month, per year) per patient
- Dose changes: increased and decreased doses of *Human-cl rhFVIII* used to treat individual BEs
For further definition of a dose change, see below (end of this chapter)
- Dose changes: in the doses per infusion and changes in the total dose used to treat subsequent BEs of the same site (e.g. elbow, knee, etc.) in the same patient.
For further definition of a dose change, see below (end of this chapter).
- Details on any concomitant medication used

* If the treatment of a BE at one bleeding site is interrupted for > 48 hours, the events are to be recorded as two separate BEs; if another than the original bleeding site is affected, the events are to be recorded as separate BEs at any time.

Definition of dose change:

A dose change will be considered relevant if the difference in the weight adjusted doses is ≥ 30 IU/kg body weight.

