## **3** INVESTIGATIONAL PLAN

## 3.1 Study Endpoints

## 3.1.1 Primary Endpoint - Immunogenicity of Human-cl rhFVIII

Immunogenicity of *Human-cl rhFVIII* is the primary endpoint. Inhibitor activity will be determined by the modified Bethesda assay (Nijmegen modification), using congenital FVIII-deficient human plasma, spiked with *Human-cl rhFVIII*, at the following time points:

- At baseline (Screening Visit)
- Every 3-4 EDs until ED 20
- Every 10-12 EDs or every 3 months ± 2 weeks (whichever comes first) after ED 20 until 100 EDs are reached
- Any time in the case of suspicion of an inhibitor development

In case of a positive inhibitor result, an inhibitor retesting, using a second separately drawn sample, should be performed. A FVIII inhibitor is defined as "positive", if the retesting confirms the positive result, otherwise the result is considered as being "negative".

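### The SAP's primary-endpoint sentence contradicts its own confirmation rule I2; the incidence outputs do not say which applies, and I2 read plainly is stricter than protocol 3.1.1

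*SAP*

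**What the plan says.** Three rules bear on the primary endpoint.

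- **SAP 3.4.1, endpoint sentence.** A patient is positive if the assay "results in a titer ≥ 0.6 BU at any time point during the observation period". A later paragraph in the section asks for a retest of any positive on a second, separately drawn sample, and "the result of the second sample will be taken as the final result for the time point".
- **Protocol 3.1.1.** An inhibitor is positive "if the retesting confirms the positive result, otherwise the result is considered as being" negative. The retest uses a second sample, drawn separately. No time limit is set for that draw.
- **SAP 3.4.1, definitions I1 to I3.** I1 confirms a high-titre inhibitor from one result ≥5 BU plus either another at a later time point or a retest ≥5 BU. Where I1 is not met, I2 offers three branches. Two need a positive, a positive retest and a positive at another time point. The third needs "inhibitor level ≥ 0.6 BU at three subsequent time points", with the qualifier "e.g. if retests are not available". A footnote explains that subsequent means later, in time or in sample, "but not necessarily the immediate consecutive visit or sample".

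Several passages point to I1 to I3 as the governing rule. The note to I3 says that a low titre which becomes a confirmed high titre "is solely counted as a high titre inhibitor". I4 starts the clock at "the date of the first positive inhibitor titre detected in a confirmed" inhibitor patient under I2. Tables 14.2.2.1 to 14.2.2.4 and listing 16.2.8.3 speak of confirmed inhibitors. SAP 9.1 and tables 14.2.1.1 and 14.2.1.2, which carry the incidence and its confidence interval, state titre cut-offs only and do not cite I1 to I3.

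**The concern.** Inhibitor incidence is the primary endpoint, and the one sentence that defines a positive patient for it disagrees with the case definition a few paragraphs below. A programmer working from 9.1 and the table titles has no instruction on which to use.

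If I1 to I3 are used, as the text suggests, the SAP has replaced the protocol's single confirming retest with a rule that, outside confirmed high titres, asks for more. A patient who meets the protocol rule but not I2 leaves the numerator and is censored in the time-to-inhibitor analysis as a patient without inhibitor. A reader of the headline figure would not know that it rests on a different rule from the protocol's.

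**Working it through.** The documents give no figure to reproduce here, so the check applies each rule to the same patients. In the first four rows ≥5 BU is not confirmed under I1.

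| Test history | Endpoint sentence alone | With SAP retest sentence | Protocol 3.1.1 | I1/I2, plain reading |
|---|---|---|---|---|
| One positive, never retested, no other positive | + | + | − | − |
| One positive, negative retest, no other positive | + | − | − | − |
| One positive, positive retest, no positive at another time point | + | + | + | **−** |
| Positive, positive retest, and a positive at another time point | + | + | + | + |
| ≥5 BU with retest ≥5 BU | + | + | + | + |

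1. *Internal conflict.* In row 1 the endpoint sentence and I2 disagree even after the retest sentence is applied, because there is no second sample to replace the first result.
2. *Departure from the protocol.* Row 3 is positive under the protocol and unconfirmed under I2. It includes a first result ≥5 BU with a retest between 0.6 and 5 BU, since I1 then fails and I2 still needs a positive at another time point.
3. *How row 3 can arise.* An inhibitor may first appear at the completion test. Or a transient one may fall below 0.6 BU before the next scheduled test, which after ED 20 can be 10 to 12 EDs or 3 months away.
4. *Wording that decides cases.*
   - If one second draw may serve as both retest and later sample, row 3 becomes positive under I2 and the departure disappears.
   - A negative retest matters in every branch. Take a patient with a positive and positive retest, then a later positive with a negative retest. Branch 1 confirms him on first results but not if the retest overrides. Three positives, each with a negative retest, pose the same question in branch 3.
   - I2 speaks of retesting the sample of a time point, which could mean a re-assay. Protocol 3.1.1 means a new draw.
5. *Size.* Inputs: N = 100 (SAP 4.2), and an inhibitor rate of up to about 30% (protocol 1.1), used for scale only. One patient is 1/100 = 1 percentage point. The exact (Clopper-Pearson) 95% limits for x of n are the 0.025 quantile of Beta(x, n − x + 1) and the 0.975 quantile of Beta(x + 1, n − x).
   - x = 30: 30%, 21.2 to 40.0
   - x = 29: 29%, 20.4 to 38.9
   - x = 27 (three patients fewer): 27%, 18.6 to 36.8

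**The case against.** The strongest defence is that I1 to I3 plainly govern: I3 says how patients are counted, I4 is tied to I2, and many outputs say confirmed. Protocol 9.2.2 also states the incidence by cut-off only, and protocol 9.2 leaves analysis details to the SAP. This largely stands on intent. It does not remove the contradictory endpoint sentence, and it does not tell the reader that the protocol's rule has changed. The data review clause in SAP 3.4.1 does not help either, since it describes only high-versus-low-titre cases.

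The completion-visit route is partly covered. Protocol 7.3.2 makes every inhibitor a serious adverse event. Adverse events are followed until resolved or stable, and persisting abnormal laboratory values until resolution or for 14 days after the final visit. A later sample is therefore likely, but it need not be a central-laboratory one or count under I2.

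Three stronger readings are tempting and not supported:

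- A reader might infer that the trial will report unconfirmed single positives as its primary result. The weight of the text is against that.
- A reader might infer that I2 is also looser than the protocol, because three unretested positives count under it. That requires that a later visit's sample never serve as the protocol's second draw. Protocol 3.1.1 sets no such limit.
- A reader might infer that the bleeding analyses are distorted, because an unconfirmed patient's time is treated as inhibitor-free. For a completion-visit positive almost no on-study time is involved, and for a transient one at most about one test interval.

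**Conclusion.** The endpoint sentence is wrong as written, because it contradicts I2 within the same section. The incidence outputs do not resolve the contradiction. If I1 to I3 govern, then on a plain reading I2 is stricter than protocol 3.1.1 for any inhibitor not confirmed at ≥5 BU under I1, so it can lower the reported incidence. The plain reading takes the retest as belonging to the same time point, as the SAP's retest sentence suggests, so that it cannot also be the later positive.

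The departure is undeclared in the text available. The SAP's front matter was not part of that text, so nothing firmer can be said.

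The number of affected patients is unknown and may be zero, and each would move the incidence by 1 point at N = 100. A retest-confirmed high titre is positive under every rule. The study is descriptive, so no error rate or power is at stake, and all titres are listed, so cases can be recovered. This should be fixed before the final figure is reported, but it does not undermine the study.

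**What to change.** 1. Replace the endpoint sentence in SAP 3.4.1 with one that refers to an inhibitor confirmed under I1 to I3. Cross-refer to I1 to I3 in SAP 9.1 and in tables 14.2.1.1 and 14.2.1.2, and declare the difference from protocol 3.1.1.
2. In I2, state for all three branches whether a negative retest overrides the first result (the SAP's retest sentence suggests that it does). Also state whether the retest is a new draw or a re-assay, and whether one second draw may serve as both retest and subsequent sample.
3. Report, as a named sensitivity analysis, the incidence with 95% CI under the protocol rule: a positive confirmed by a second, separately drawn sample. State whether a later visit's sample counts as that second draw, and keep patients confirmed as high titre under I1 positive. List every patient whose status differs between the rules, including those first positive at their last test.

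The cost is a few SAP sentences, one table and one listing, with no new data. The I1 to I4 framework stays, so no new primary case definition is introduced after the interim analysis. The downside is that two incidence figures will be shown, and they may differ by a few points.

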6.4.3 Interim Analyses and Data Monitoring

One interim analysis was conducted.

The interim analysis comprised the complete analysis as planned for the final analysis, except for the Health economic modeling analysis, the resource use data, RNA expression and Epitope mapping data, and the PK analyses for patients receiving ITI. All analyses were based on available data at that time.

Time-Point of Analysis

Interim analysis: once 50 patients achieved at least 50 EDs.

For the interim analysis the data to be analysed was frozen in a data snapshot for the analysis.

The final statistical analysis was conducted upon successful completion of all database release (DBR) procedures and sign-off of the DBR release form.

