8 EVALUATION OF TREATMENT COMPLIANCE AND EXPOSURE

Prophylaxis, ITI treatment and treatment of Bes and surgeries: The following will be tabulated and/or summarized:

- Reason for Administration
- Number of Injections
- First dose, last dose, number of Exposure Days
- Total Dose (IU)
- Dose (IU FVIII/kg BW)

Furthermore, the *Human-cl rhFVIII* batches used will be listed for both assays with their potencies in the listings for doses.

9 **EVALUATION OF TREATMENT EFFICACY**

9.1 **Immunogenicity**

All recorded determinations of inhibitors against FVIII will be listed. The absolute number and cumulative incidence of inhibitors (inhibitor titre ≥ 0.6 , < 5 BU and ≥ 5 BU respectively) will be presented in total, and as percentage of the analysis population, with a 95% confidence interval. If justified by the number of events, the time period until the first inhibitor activity will be tabulated and displayed graphically by means of a Kaplan-Meier plot of percentages without inhibitor versus cumulative EDs until appearance of inhibitor, and a logistic regression analysis of incidence rates of FVIII inhibitor development will be performed (prognostic factors: family history of inhibitor, family history of hemophilia, weight, mean dose/ED, age, F8 gene mutation defect (including null/non-null, high/low risk mutation analysis), number of EDs before inhibitor development, age at first treatment, intensity of treatment (number of peak treatment moments), country ethnicity, center).

In addition, number of EDs until inhibitor development will be shown in life-table lists showing the incidence of inhibitors per interval of 5 EDs; a Cox regression will analyse the ED to inhibitor data for the impact of possible prognostic variables (same list as for logistic regression analysis above).

The incidence of low and high titre FVIII inhibitors will also be presented grouped by ethnicity and F8 gene mutations categorized as null/non-null and as high/low risk, incl. results of the immunogenotyping sub-study. For the combined presentation of subgroup results, Forest plots will be provided.

The number of EDs before inhibitor development will be tabulated for each patient with FVIII inhibitors.

RNA expression analysis data and Antitope Ltd. sub-study data will not be analysed under this SAP.

9.2 **Prophylaxis (Prevention of Bleeding episodes)**

The following will be presented following the manners of representation described in section 6:

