14.2.2.4	T	Statistics on the number of EDs before first confirmed inhibitor activity in patients with low titre inhibitors by intensity of treatment	ITT, PP
14.2.2.5	T	Statistics on the number of EDs before first inhibitor activity in patients with any inhibitors – by reason of treatment (on-demand, prophylaxis, combinations)	ITT, PP
14.2.2.6	T	Statistics on the number of EDs before first inhibitor activity in patients with only high titre inhibitors (on-demand, prophylaxis, combinations)	ITT, PP
14.2.2.7	T	Statistics on the number of EDs before first inhibitor activity in patients with only low titre inhibitors- by reason of treatment (on-demand, prophylaxis, combinations)	ITT, PP
14.2.3.1-3	F	Kaplan-Meier curves on number of EDs until first inhibitor activity (any inhibitor, high titre inhibitor, low titre inhibitor,)	ITT, PP
14.2.3.4-6	T	Kaplan-Meier curves on number of EDs until first confirmed inhibitor activity – Display of product limit estimates (any inhibitor, low titre inhibitor, high titre inhibitor)	ITT, PP
14.2.4.1-3	F	Kaplan-Meier curves on number of EDs until first inhibitor activity by F8 mutation type, null and non-null mutation (any inhibitor, high titre inhibitor, low titer inhibitor)	ITT, PP
14.2.4.4-6	T	Kaplan-Meier curves on number of EDs until first inhibitor activity by F8 mutation type, null and non-null mutation (any inhibitor, high titre inhibitor, low titer inhibitor) – Display of product limit estimates	ITT, PP
14.2.4.7-9	T	Life-tables : Risk of inhibitor incidence over time in steps of 5 EDs (any inhibitor, high titre inhibitor, low titer inhibitor) – Display of life-table estimates	ITT, PP
14.2.5	T	Logistic regression analysis for any, low- and high-titre inhibitors (prognostic factors: family history of hemophilia, family history of inhibitors, weight, mean dose/ED, age, F8 gene mutation defect, null/non-null mutation, number of EDs before inhibitor development, age at first treatment, intensity of treatment, country, center, ethnicity)	ITT, PP
14.2.6	T	Cox regression analysis for any, low- and high-titre inhibitors (initial model with same prognostic variables like in 14.2.5)	ITT, PP
14.2.7	T	Statistics on the number of exposure days and injections administered for ITI treatment with Human-cl rhFVIII	ITI
14.2.8	T	Statistics on the amount of Human-cl rhFVIII (IU) for ITI treatment per month, per year, per exposure day, per injection and in total	ITI

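### The high- and low-titre Kaplan-Meier curves censor each other's events, so they can overstate incidence by exposure day (about 1.1 to 1.3 points per class at 30% any inhibitor, assuming a 60:40 split)

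*SAP*

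**What the plan says.** Definition I3 in SAP section 3.4.1 assigns each confirmed inhibitor patient to one titre class over the whole observation period. A low-titre inhibitor that later becomes confirmed high titre counts only as high. The SAP adds: "The patient cannot be counted twice".

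The same section then sets the censoring for the class-specific time-to-event analyses:

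- High titre: "For this analysis patients with confirmed low titre inhibitor will be censored at date" of first detection.
- Low titre: "For this analysis patients with confirmed high titre inhibitor will be censored at minimum" of the two possible first-detection dates.

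The SAP section 13 output list applies this to:

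- Figures 14.2.3.1-3: "Kaplan-Meier curves on number of EDs until first inhibitor activity (any inhibitor, high titre inhibitor, low titre inhibitor".
- Tables 14.2.3.4-6, with product-limit estimates: "Kaplan-Meier curves on number of EDs until first confirmed inhibitor activity".
- Figures 14.2.4.1-3 and Tables 14.2.4.4-6, the same displays by F8 mutation type.
- Life tables 14.2.4.7-9. SAP section 9.1 says the number of EDs until inhibitor development "will be shown in life-table lists showing the incidence of inhibitors per interval of 5 EDs". No cumulative column is named.

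Neither document plans a competing-risk estimator. Crude numbers and percentages by titre class, with 95% confidence intervals, are planned separately (SAP section 9.1; Tables 14.2.1.1-2).

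**The concern.** Because I3 makes the classes exclusive, a patient finally classed as low titre can never have the high-titre event, and the reverse. Each class is a competing event for the other. Kaplan-Meier with the other class censored treats those patients as if their risk continued like that of patients still under observation, whereas under the SAP's own definition it is zero.

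A reader may take one minus the high-titre curve at a given ED as the probability that, by that ED, a patient has had first detection of an inhibitor that ends up classed as high titre. As planned, the curve can exceed that probability. The two class curves can also contradict the any-inhibitor curve in the same figure set, because their complements can add to more than its complement. The effect grows with incidence, so it would be larger in a high-incidence stratum such as the null-mutation curves.

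**Working it through.** **Inputs.** The documents give no class-specific incidence, so there is no planned figure to reproduce.

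- Number of patients: 100 (protocol section 2.1, SAP section 4.2).
- Any inhibitor, *p*: 30%, the upper figure in protocol section 1.1; 20% as a sensitivity value. As an illustration of a high-incidence stratum only, 43%, which SAP section 2 quotes for null mutations in another trial's recombinant-FVIII group. It is not this trial's expectation.
- High-titre share of inhibitors, *s*: an assumption, 60:40, range 50:50 to 67:33.

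**Step 1. Closed form.** Assume proportional cause-specific hazards, no ties and no other loss. Then

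- 1 − KM(high) = 1 − (1 − *p*)^*s*, against a true incidence of *s·p*;
- 1 − KM(low) = 1 − (1 − *p*)^(1 − *s*), against (1 − *s*)*·p*.

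For *p* = 0.30 and *s* = 0.6: 1 − 0.7^0.6 = 19.27% against 18%, and 1 − 0.7^0.4 = 13.30% against 12%.

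| *p* | Split | High: 1 − KM / true (%) | Low: 1 − KM / true (%) | Sum minus *p* (points) |
|---|---|---|---|---|
| 20% | 60:40 | 12.53 / 12.00 | 8.54 / 8.00 | 1.07 |
| 30% | 50:50 | 16.33 / 15.00 | 16.33 / 15.00 | 2.67 |
| 30% | 60:40 | 19.27 / 18.00 | 13.30 / 12.00 | 2.56 |
| 30% | 67:33 | 21.16 / 20.00 | 11.21 / 10.00 | 2.37 |
| 43% | 60:40 | 28.6 / 25.8 | 20.1 / 17.2 | 5.76 |

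**Step 2. Ties.** Inhibitors are found at scheduled tests, so both classes can appear on the same ED, which reduces the effect. Take 100 patients, no dropout, and (high, low) counts at seven successive tests of (4,2), (4,3), (3,2), (2,1), (2,1), (2,2), (1,1). The numbers at risk are 100, 94, 87, 82, 79, 76 and 72.

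- High: 1 − (96/100)(90/94)(84/87)(80/82)(77/79)(74/76)(71/72) = 18.97%, true 18%.
- Low: 1 − (98/100)(91/94)(85/87)(81/82)(78/79)(74/76)(71/72) = 13.20%, true 12%.
- Any: 30.00%. Excess: 18.97 + 13.20 − 30.00 = 2.17 points.

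**Step 3. Order of events** (18 high, 12 low, 100 patients).

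- All on one ED: 18.0% and 12.0%, no excess.
- All high first: 18.0% and 12/82 = 14.6%.
- All low first: 18/88 = 20.5% and 12.0%.

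A class is overstated only if some of its events follow events of the other class.

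**Step 4. Simulation.** 100 patients, 1,500 runs per cell, exponential onset with mean 15 EDs (assumed), detection at the next test. Mean sum excess at 60:40, in points:

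| *p* | No ties | Individual 3-4 then 10-12 ED schedules | One common test grid |
|---|---|---|---|
| 20% | 1.05 | 1.01 | 0.92 |
| 30% | 2.54 | 2.48 | 2.21 |
| 43% | 5.72 | 5.46 | 5.00 |

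At 30%, the splits from 50:50 to 67:33 give 2.03 to 2.65. With 20% independent dropout (30%, 60:40, common grid, 3,000 runs), the high-titre results are crude 17.4%, Aalen-Johansen 18.0% and 1 − KM 19.1%; the sum excess is 2.2.

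**Step 5. Scale.** The sum excess at 30% and 60:40 is 2.2 to 2.6 points; halved, 1.1 to 1.3 per class on average. The exact 95% confidence interval of 18/100 is 11.0% to 26.9%, with half-width (26.9 − 11.0)/2 = 7.95. The ratios are 1.1/7.95 = 0.14 and 1.3/7.95 = 0.16, about one seventh to one sixth.

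**Step 6. Life tables.** An interval risk is not a cumulative estimate, so the main point applies only if a cumulative column is shown. The usual actuarial denominator still shifts the interval risk slightly: with 6 high and 4 low among 100 at risk, 6/(100 − 4/2) = 6.12% against 6.00%.

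**The case against.** The strongest reply is that no planned headline result is wrong. Inhibitor incidence by class is reported as a count and percentage with a confidence interval. SAP section 9.1 describes the Kaplan-Meier display as the proportion free of inhibitor, and only if event numbers justify it. All analyses are exploratory, and no text says the class curves will be read as incidence or added together. This stands, and it is why the point is minor. It does not remove it: class-specific curves against cumulative EDs invite that reading, and the crude percentages do not show incidence by ED. The crude percentages are unaffected by this censoring rule, but they are not free of error under dropout (17.4% against 18.0% in Step 4).

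Second, cause-specific censoring is standard. That is right for the Cox models, where it should stay. It does not justify reading one minus Kaplan-Meier as incidence.

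Third, definition I4 and the text after it date a high-titre inhibitor from the first positive test, even if that test was below 5 BU. The curve therefore describes first detection of an inhibitor eventually classed as high titre, not the time of reaching 5 BU. This also stands. Aalen-Johansen on the same dates keeps that meaning and should be labelled accordingly.

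Fourth, the size rests on assumptions. The 1.1 to 1.3 points are an average over the two classes; in the tied example the high-titre excess is 0.97. At 75:25 the closed form gives 0.97 to 1.03 per class. If one class comes entirely first at 60:40, the excess is zero for that class and about 2.5 to 2.6 for the other. The 43% case comes from another trial, and a mutation stratum would have fewer than 100 patients and wider intervals.

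**Conclusion.** The concern holds as a minor point. Followed exactly, SAP section 3.4.1 produces high- and low-titre curves whose complements can overstate incidence by ED and can add to more than the any-inhibitor figure. At 30% any inhibitor the sum excess is 2.2 to 2.6 points with a 60:40 split, and 2.0 to 2.7 over splits from 50:50 to 67:33. At 20% and 60:40 it is 0.9 to 1.1. In a stratum at 43% it would be 5.0 to 5.8, or 2.5 to 2.9 per class on average. These figures assume the split and similar timing of the two classes, neither of which the documents give.

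The affected outputs are Figures 14.2.3.2-3 and 14.2.4.2-3 and Tables 14.2.3.5-6 and 14.2.4.5-6, plus life tables 14.2.4.8-9 if they show a cumulative estimate. The censoring rule does not affect Tables 14.2.1.1-2, the any-inhibitor curves or the cause-specific Cox models.

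**What to change.** In SAP section 3.4.1, state that high- and low-titre incidence by ED is estimated with the Aalen-Johansen cumulative incidence function, with the other titre class as a competing event. Only inhibitor-free patients are censored, at their last inhibitor test. Use this for the four figures and four tables named in the verdict, and label onset as first detection of an inhibitor eventually classed as high or low titre. Keep Kaplan-Meier for any inhibitor and the present censoring for the Cox models.

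If the life tables show a cumulative column by titre class, compute it as competing-risk cumulative incidence, label the interval risks as cause-specific, and note that they do not multiply through to that column.

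The cost is one SAP paragraph and a standard procedure option, with no new data. The downside is comparability with the interim report: "The interim analysis comprised the complete analysis as planned for the final analysis", apart from listed exceptions that do not include these displays. Either note the change of estimator in the study report or re-run the interim curves. A re-run is possible because "For the interim analysis the data to be analysed was frozen in a data snapshot for the analysis".

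If the estimator is not changed, the minimum is to label the class curves as cause-specific and state that their complements are not incidence by ED. That is cheaper, but it leaves no valid display of class-specific incidence by ED.
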